## 1. Synopsis

Sponsor/ Manufacturer	Ivoclar Vivadent AG [name] Fürstentum Liechtenstein
Study Title	Evaluation of Effectiveness of a Novel Remineralizing Agent: A Randomized Controlled Clinical Trial
Short Title	n.a.
Version/ Date	1.0/ 21.03.22
Registration:	https://clinicaltrials.gov
Clinical investigation category and Rationale	Medical Device Clinical Trial
Background and Rationale:	Active non-cavitated caries lesions on buccal surfaces teeth scored with ICDAS code 1 or 2 are characterized by white chalky appearance as a result of loss of minerals from the tooth structure. The progression of these lesions can be reversed or arrested by application of some therapeutic agents, enhancing remineralization. Fluoride varnishes are considered to be the first choice of treatment for this purpose. Fluoride varnishes with high concentration of fluoride provides calcium fluoride formation which acts as a reservoir for both calcium and fluoride. The release of these ions during acidic challenges inhibits further dissolution of hydroxyapatite crystals of the dental hard tissues. In the present pilot clinical study, the test material containing - calcium fluoride nanosol in addition to high level of ammonium fluoride content will be evaluated. Ammonium fluoride solution and calcium fluoride solutions are designed to be applied separately to form a protective layer. Application of calcium fluoride in combination with high concentration of fluoride is anticipated to have beneficial effects on the repair of incipient caries lesions with ICDAS code 1 and 2.
Objective(s):	Comparison between investigational medical device (Exp. Fluoride Appl. Ivoclar-Vivadent AG, Schaan, LI) and control product (Fluor Protector S, Ivoclar-Vivadent AG, Schaan, LIE)
Outcome(s):	Primary outcome:

	

Evaluation of the change in lesion size and mineral content based on Qraycam measurements at baseline, after 1, 6 and 12 months.

 
Secondary outcome:
 

Clinical evaluation of the lesion progression according to ICDAS and Nyvad criteria at baseline, 1, 6 and 12 months.

Digital pictures for secondary evaluation by the observers to calculate inter-examiner reliability.

Clinical investigation design:	Randomized controlled blinded evaluation in split-mouth design
Inclusion / Exclusion criteria:	
At least two early caries lesions (arrested or progressive) on buccal sides of two teeth in two different quadrants.
 
Inclusion criteria:
 

Subjects are required to have at least two active non-cavitated white spot lesions (WSLs) on buccal surfaces of anterior teeth or premolars (ICDAS code 1 and 2; Nyvad score 1)

Age between 13 and 50 years

No untreated caries lesions or periodontal disease

No systematic disease or medication (such as antidepressants, antibiotics etc.) that affects salivary flow rate

Subjects claimed regular brushing at least twice a day

Subjects had to agree to keep the scheduled recall appointments for 1 year.

 
Exclusion criteria:
 

Inactive non-cavitated lesions (Nyvad Score 4)

Lesions with microcavity, cavitation, chipping or discoloration

Lesions at buccal side of the molars

Lesions adjacent to restoration

Developmental white spot lesions such as enamel hypoplasia

	

• Pregnant and breastfeeding women

Intervention: Measurements and procedures	The investigational medical device Experimental Fluoride Application, consists of an aqueous fluoride solution and an ethanol-based solution of calcium fluoride nanosol, which is supplied in two separate bottles which will be applied directly on enamel.
Control Intervention (if applicable):	Fluor Protector S (Ivoclar Vivadent AG, Schaan, Liechtenstein) is a protective varnish containing ammonium fluoride. It will be applied on enamel of teeth in the control group. The application is according the instruction for use within the indication.
Number of Participants with Rationale:	23, rationale see statistical considerations
Duration of the investigation:	6 months estimated duration for the main investigational plan (e.g. from start of screening of first participant to last participant processed and finishing the clinical investigation) 1 year 6 months of First-Participant-In until Last-Participant-Out
Investigation Schedule:	Intervention, 4 weeks, 6 months, 12 months recall
Study Coordinator:	[name] [name]. Dr. h.c., Ph.D, University of Zurich Division of Dental Biomaterials Center of Dental Medicine Clinic of Reconstructive Dentistry [name] Mobile: [REDACTED] E-mail: [REDACTED]
Principal Investigator:	[name] [name] Istanbul Medipol University School of Dentistry Department of Restorative Dentistry [name] E-mail: [REDACTED]
Investigation Site(s):	Single-centre
Statistical Considerations:	t-test allows a sample size of 23 patient with power of 80% at a significance level of 5%.

Compliance Statement:	This clinical investigation will be conducted in compliance with the CIP (protocol), the current version of the Declaration of Helsinki, ISO EN 14155, ICH-GCP (as far as applicable) as well as all national legal and regulatory requirements.
------------------------------	--

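### The stated 80% power is attached to the same 23 patients who are to be enrolled, with no allowance for loss over 12 months; unless 23 hides a margin, 80% is a zero-loss figure

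*Combined protocol and SAP*

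**What the plan says.** All the relevant text is in section 1, Synopsis, apart from the visit table in section 3, Study Schedule.

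- **Statistical Considerations:** "t-test allows a sample size of 23 patient with power of 80% at a significance level of 5" per cent. The row gives no difference, SD or standardised effect. It does not say whether the test is paired or one- or two-sided, or at which visit it is applied.
- **Number of Participants with Rationale:** "23, rationale see statistical considerations". The planned number is the powered number, and the only reason given is the row above.
- **Clinical investigation design:** "Randomized controlled blinded evaluation in split-mouth design". Each patient supplies both treatments.
- **Inclusion criteria:** "Subjects are required to have at least two active non-cavitated white spot lesions (WSLs) on buccal surfaces of anterior teeth or premolars", so two lesions is a minimum. Another criterion reads "Subjects had to agree to keep the scheduled recall appointments for 1 year".
- **Outcomes and schedule:** the primary outcome is change on Qraycam, measured at baseline and at 1, 6 and 12 months. No visit is named as primary.

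The text reviewed (synopsis, definitions, study schedule) contains no expected loss rate, no inflation of the sample size, no replacement rule and no rule for missing data.

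**The concern.** A sample-size calculation gives the number of evaluable patients needed. When enrolment is set at exactly that number and patients are followed for a year, the stated power describes the case in which nobody is lost. Agreement at entry to attend recalls helps retention, but it is not an allowance in the calculation.

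The split-mouth design sharpens this. A patient who withdraws takes both sides of the comparison with them, so each withdrawal removes a full unit of the paired analysis.

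What is at stake is how a null result is read. If the trial ends with 20 or 18 evaluable patients and no significant difference, a reader of the plan will judge that result against 80% power, which the trial may not have had.

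**Working it through.** **Inputs.** N = 23, power 80% and significance level 5% come from Statistical Considerations. Pairing is inferred from the split-mouth design. Two-sided testing is an assumption. Effect size, SD and loss rate are not stated.

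**Step 1: the plan's own figure.** The 23 cannot be reproduced from first principles, because no effect size or SD is given. It can only be solved backwards.

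For a paired t-test with n patients and standardised within-patient difference d (mean difference divided by the SD of the differences):

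power = P(T > t(0.975, n−1)), where T is noncentral t with n−1 degrees of freedom and noncentrality d√n. The opposite tail is negligible.

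Setting power = 0.80 at n = 23 (critical value 2.074) gives noncentrality 2.932, so d = 2.932/√23 = 0.611.

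**Step 2: power at the same d with fewer evaluable patients.**

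| Evaluable | Lost of 23 | Critical t | 0.611 × √n | Power |
|---|---|---|---|---|
| 23 | 0 | 2.074 | 2.93 | 80.0% |
| 22 | 1 (4%) | 2.080 | 2.87 | 78.1% |
| 21 | 2 (9%) | 2.086 | 2.80 | 76.0% |
| 20 | 3 (13%) | 2.093 | 2.73 | 73.7% |
| 19 | 4 (17%) | 2.101 | 2.66 | 71.2% |
| 18 | 5 (22%) | 2.110 | 2.59 | 68.6% |

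**Step 3: does rounding up rescue it?** If 23 is the smallest whole number reaching 80%, d lies between 0.611 and just under 0.626, the value at which 22 would suffice. At the upper end power is 81.9% with 23, just under 80.0% with 22, 75.7% with 20 and 70.7% with 18. Rounding therefore gives at most about two points.

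**Step 4: does the unstated test variant matter?** Solving each variant for 80% at 23 and then dropping to 22:

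- paired, one-sided (d = 0.535): 78.3%
- two-sample with 23 per arm, two-sided (d = 0.845): 78.1%
- two-sample with 23 per arm, one-sided (d = 0.745): 78.4%

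The loss per patient is nearly the same in every case.

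**Step 5: could 23 already contain a margin?** Yes, arithmetically. 21/(1 − 0.05) = 22.1, rounded up to 23; 20/(1 − 0.10) = 22.2, also rounded up to 23. The d that gives exactly 80% would then be 0.643 at 21 patients or 0.660 at 20, instead of 0.611. Without a stated effect size the text cannot separate these cases.

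**The case against.** The strongest counter-argument is Step 5: the plan never says that 23 is the minimum evaluable number. A reader might infer that any single withdrawal is certain to take the trial below 80%. The documents do not support that, because an unstated margin cannot be excluded. The point therefore has to be conditional. It is not removed, since the row attaches 80% to 23 itself and mentions no margin.

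Other tempting inferences also go too far.

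- **That any lost lesion removes a patient.** Two lesions is the minimum for entry. A patient with more could lose one and still contribute to a patient-level comparison. The loss is decisive only where the patient has a single pair, and the text does not say how extra lesions are used.
- **That any missed recall removes a patient from the primary comparison.** No primary visit is named. A missed recall removes data at that visit, and how visits are combined is not stated.
- **That the calculation is wrong or that 23 is too few.** No figure in the text is shown to be in error. This is an omission.

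Three points of proportion also stand. One loss costs about two percentage points. The study calls itself a pilot, although it still claims 80% power, and that claim should be accurate. The missing effect size and SD are the larger defect: without them, 80% power has no stated target. They belong in the same row, so the fix asks for them.

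One could instead raise enrolment. Keeping 23 evaluable would need 25 patients at an assumed 5% loss (23/0.95 = 24.2), 26 at 10% (25.6), 28 at 15% (27.1) and 29 at 20% (28.75). That is a legitimate choice for the sponsor, but it adds patients, and the stated power can be made accurate without it.

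**Conclusion.** The point holds in conditional form. The powered number and the planned number are both 23, and the text reviewed makes no allowance for loss over 12 months. Unless 23 includes an unstated margin, 80% is the best case and not the expected one. Power would be about 78% with 22 evaluable patients, 74% with 20 and 69% with 18, or at most just under 80%, 76% and 71% if 23 is a rounded-up minimum.

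These figures assume a two-sided paired t-test at 5%, one within-patient comparison per patient, and the standardised difference of 0.61 that the plan's own numbers imply. Because no loss rate is given, they are a range and do not predict what the trial will achieve. The matter should be corrected, but it does not invalidate the design.

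**What to change.** 1. **Statistical Considerations row.** Keep enrolment at 23 and restate the power along these lines: *80% power if all 23 patients are evaluable at the analysed visit; about 74% with 20 and 69% with 18 (two-sided paired t-test, 5%, same standardised difference)*. Give the assumed effect size and SD beside it, and recompute the three percentages if the sponsor's actual test or effect differs from these assumptions.
2. **If 23 already includes a margin,** state instead the evaluable number that gives 80% and the loss assumed.
3. **Participants row.** Change it to *23 enrolled*.
4. **Reporting.** State that the number of evaluable patients will be reported at each visit.

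Whether lost patients are replaced is a design decision on which the text is silent; this fix does not depend on it.

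The cost is wording only, with no extra patients or visits. The stated power becomes less favourable, and the sponsor has to disclose the effect size and SD behind the 23.

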## 2. Definitions, Terms, Abbreviations

ADE	Adverse Device Effect. Adverse events (see below) that are related to the MD under investigation or the comparator and to the procedures involved. For users or other persons this is restricted to events related to the MD.
AE	Adverse event (Art. 2 Abs 57 MDR): Any untoward medical occurrence, unintended disease or injury or any untoward clinical signs (including an abnormal laboratory finding) in subjects, users or other persons whether or not related to the MD.
Castor EDC	Electronic data capturing (EDC) platform from the company Castor
CE	Conformité Européenne (Label on products complaint to European Medical Device Legislation)
CER	Clinical Evaluation Report
CIP	Clinical Investigation Plan
CIR	Clinical Investigation Report
Clinical studies	Systematic investigation in one or more human subjects, undertaken to assess the clinical performance, effectiveness or safety of a medical device. Note: For the purpose of this document, "clinical investigation" or "clinical trial" are synonymous with "clinical study"
DD	Device Deficiency (Art. 2 Abs 59 MDR): Inadequacy of a medical device related to its identity, quality, durability, reliability, safety or performance, of an investigational device, including malfunction, user errors and inadequate information supplied by the manufacturer. The definition includes deficiencies related to the investigational MD or the comparator MD.
(e)CRF	(electronic) Case Report Form
ICH-GCP	International Conference on Harmonisation – Good Clinical Practice
IB	Investigator's Brochure
ICF	Informed Consent Form
ISO	International Organization for Standardization
MD	Medical Device
Directive)	
PI	Principal Investigator
SAE	Serious adverse event: (Art. 2 Abs 58 MDR) Any adverse event (see definition above) that led to any of the following:

- (a) death,
- (b) serious deterioration in the health of the subject that resulted in any of the following:
  - (i) life-threatening illness or injury,
  - (ii) permanent impairment of a body structure or a body function,
  - (iii) hospitalization or prolongation of patient hospitalization\*,
  - (iv) medical or surgical intervention to prevent life-threatening illness or injury or permanent impairment to a body structure or a body function,
  - (v) chronic disease,
- (c) foetal distress, foetal death or a congenital physical or mental impairment or birth defect.

\*Note: planned hospitalization for pre-existing condition, or a procedure required by the CIP, without a serious deterioration of the health status of the subject, is not considered an SAE

Suspected Serious Device Effect.

SAE related to the MD and/or the comparator

Participants (i.e. Patients) that are included in a clinical investigation.

SADE  
Subjects

### 3. Study Schedule

Study Periods	Screening, Patient information	Treatment, Intervention (Enrolment)	Follow-Up (Recall)		
Visit	1	2 x	3	4	5
Time (hour [h], day [d], week [wk], month [mt])	12 mt	1 h	4 w	6 mt	12 mt
Patient Information	x				
Informed Consent	x				
Medical History	x				
In- /Exclusion Criteria	x	x			
Tooth Examination	x				
Vitality test	x				
VAS for tooth sensitivity	x				
Intraoral pictures		x	x	x	x
Recording ICDAS and Nyvad scores		x	x	x	x
Professional cleaning of tooth surface		x			
QrayCam Pro measurement		x	x	x	x
Adverse events (incl. SAE)	x	x	x	x	x
Concomitant medications	x	x	x	x	x
